significantly, and therefore increased incidence of metastatic PCa and disease specific mortality is expected, beginning in approximately 2017 (11). In addition, inefficient diagnosis algorithms and unreliable risk prediction leads to "overtreatment"—it is estimated that, for 30–40% PCa patients, prostatectomy does not impact survival but exposes them to significant complications (impotence and incontinence). There is a critical and immediate need for accurate and non-invasive diagnostic tools to improve PCa diagnosis and grading. At the time of initial diagnosis, we need a diagnostic tool for evaluation of the entire prostate, to identify PCa foci, and to differentiate clinically significant cancer (requires aggressive treatment) from indolent disease (does not require aggressive treatment), to reduce financial, logistical, and emotional costs from PCa and improve the outcome of PCa management.

Currently there is no consensus on the definition of clinically significant prostate cancer. In this proposal we define significant cancer based on pathologic criteria. For biopsy, based on the Canadian recommendations (12), clinically significant cancers include all tumors with Gleason score >6 (3+3) (ISUP grade group 1), and with Gleason score ≤6 (3+3) (ISUP grade group 1) if not localized.

Multi-parametric MRI (MP-MRI) is an MRI protocol optimized for PCa and embraced worldwide by the radiology community. MP-MRI is a combination of two or more of the following imaging sequences: T₂-weighted (T₂w), diffusion-weighted (DW), and dynamic contrast enhanced (DCE). One promising solution for improving PCa detection is targeted biopsy of the prostate using MP-MRI. When performed by experts, Mp-MRI targeted biopsies result in higher detection rates of clinically significant cancer with a reduced upgrading of cancers at surgery, improving confidence in the biopsy results (13–16). MR-targeted biopsies can be performed either by fusing MR images to real time US images or directly under MR guidance (in-bore MR guided biopsy).

A.1 Current status and shortcomings of prostate magnetic resonance imaging (MRI)

Performance of MRI-targeted biopsy depends on accurate and reproducible interpretation of MR images leading to accurate identification of targets for biopsy. Images from MP-MRI are complementary and synergistic in diagnostic information, but they are also complex and difficult to decipher by radiologists. T₂w and DW MR images are the mainstay of MP-MRI, and can depict PCa with high sensitivity. T₂w and DW-MRI are the main imaging techniques for PI-RADS, the standardized reporting approach to MP-MRI (17). Currently, all commercially available PCa MP-MRI protocols are based on subjective and qualitative interpretation by radiologists, and none is truly quantitative, well defined, and reproducible. Interpretation of prostate MP-MRI varies greatly among radiologists, because of a lack of reproducible and quantitative MRI acquisition protocols, and because of a lack of decision support system (DSS) tools to assist radiologists interpret the images. This problem is exacerbated by limited number of radiologists who have substantial experience and expertise in interpretation of prostate MP-MRI. Success of MP-MRI achieved in select centers of excellence cannot be reproduced easily worldwide. **We propose to evaluate a quantitative prostate MRI acquisition protocol, and a novel Risk Map DSS tool for image interpretation, to enable widespread clinical translation of PCa MRI.** If these emerging results are reproduced widely, MRI has the potential to revolutionize PCa management, reduce unproductive biopsies and

unnecessary radical therapies (e.g., prostatectomy and radiation), and achieve more accurate and efficient diagnosis, effective follow-up, and targeted eradication of aggressive disease.

We will use a new MRI technique to obtain quantitative tissue composition maps based on a new hybrid multi-dimensional MRI (HM-MRI) approach that combines T2 and ADC measurements and detects tissue heterogeneity at the microscopic level in an innovative way.

Our group has developed two novel approaches that have potential to substantially improve multi-parametric MRI in prostate: the kT-T2 sequence (18-21) and the hybrid multi-dimensional MRI (HM-MRI) (22-25). The kT-T2 sequence provides a direct assessment of the prostatic micro-environment and HM-MRI provides an assessment of the prostatic tissue micro anatomy which allows us to find water signals that are characteristic of cancers. This is important new information that **cannot be obtained** from conventional T2 and ADC measurements.

HM-MRI data can be analyzed to produce accurate tissue composition maps showing volume fractions of stroma, epithelia, and lumen. These maps have been shown in preliminary studies from this laboratory to enhance diagnostic accuracy (26) , as summarized in Preliminary Results (**Section A.3.1.**). Information from these tissue composition maps will be incorporated into the DSS tool.

A.2. Protocol overview:

We propose to test a Risk Map DSS image interpretation tool for automated interpretation of prostate MR using research sequences, which will include quantitative kT-T₂, and HM-MRI acquisition, in the clinical MRI protocol. This will also allow straightforward comparison of kT-T2 and HM-MRI vs. conventional T2 and ADC images. This, in turn, will be used for reliable determination of clinically significant cancer in prostate which will be targeted by MR-targeted biopsies at the time of diagnosis. The goal is to achieve clinical translation of advanced and innovative technology for accurate and reliable PCa diagnosis, to provide patients and treating physicians with quantitative and objective data, and to enable them to make informed treatment decisions.

A.3. Preliminary results:

Preliminary results and research accomplishments directly related to this proposal are listed below.

A.3.1. Tissue composition estimate from HM-MRI data, and correlation with histology:

		Study	Stroma (%)	Epithelium (%)	Lumen (%)
Normal Peripheral Zone Tissue	Langer et al 2010	38.2	31.2	29.6	
	Chatterjee et al 2016	38.3±1.4	32.0±1.5	30.1±1.2	
	HM-MRI	39.0±13.6	21.5±4.6	39.4±14.1	
Prostate Cancer	Langer et al 2010	38.6	46.2	13.5	
	Chatterjee et al 2016	27.9±1.0	60.9±1.9	11.2±1.1	
	HM-MRI	37.2±9.1	48.8±9.2	14.0±5.2	

PCa from normal tissue was 0.99 for epithelium, 0.80 for lumen, 0.79 for stroma, and 0.71 for T_2 (AUC for ADC was not evaluated because cancer ROIs were outlined in ADC maps). These results suggest that HM-MRI non-invasively provides 3-dimensional information that is similar to the information obtained from 2D *ex vivo* histology slices, and that prostate tissue composition measured non-invasively by using HM-MRI have potential to improve PCa diagnosis and assessment of PCa aggressiveness. The study also resulted in a filed patent application (30).

A.3.2. PCa risk maps derived from quantitative MRI data

We have developed a preliminary risk map based on mpMRI: ADC, T_2 , and DCE signal enhancement rate (α). These parameters were calculated on a voxel-by-voxel basis for the entire, co-registered prostate. Each parameter was normalized (to 0-100) with low T_2 , low ADC, and high α signify high risk. The final risk score is a weighted sum of the parameters (ADC 40%, T_2 40%, DCE 20%) with higher risk for low T_2 , low ADC, and high α values. We analyzed preoperative 3T mpMRI of 22 PCa patients, and used five patients as the training set to find the optimal threshold for predicting PCa and 17 patients as the test set. A sector-based analysis (18 sectors per prostate) on the 17 test patients showed the following PCa detection performance: sensitivity 75% (105/140), specificity 89% (147/166), positive predictive value 85% (105/124), negative predictive value 81% (147/182), and AUC 0.82 (95% CI [0.77, 0.87]). Importantly, the risk map correctly identified all index lesions. This study suggests that the risk map can detect PCa and guide targeted biopsies for improved PCa diagnosis.

A.3.3. Pilot DSS study:

We developed a pilot DSS based on T_2 w and DW-MRI (31). A radiologist and a pathologist identified 104 ROIs (61 cancer and 43 normal tissue) based on correlation of histological and MR findings. AUC values in the differentiation of PCa from normal tissue foci of 10th percentile ADC, average ADC and T_2 w skewness were 0.92, 0.89, and 0.86 respectively. The combination of the 10th percentile ADC, average ADC, and T_2 w skewness yielded an AUC value of 0.95 for the same task. Gleason score correlated moderately with the 10th percentile ADC ($p=-0.34$, $p=0.008$) and with the average ADC value ($p=-0.30$, $p=0.02$). The combination of 10th percentile ADC, average ADC, and T_2 w skewness were promising in differentiation of PCa from normal tissue, and ADC image features correlated moderately with Gleason score (31).

A.3.4. Validation study of pilot DSS:

We validated the pilot Risk Map DSS on preoperative 1.5T MP-MR images (with endorectal coil) of 119 PCa patients (GE scanners, $n=71$; Philips scanners, $n=48$) and 265 PCa and normal peripheral zone ROIs identified through histology-MR consensus review (32). AUC values of the pilot DSS image features combined were 0.95 and 0.88

on the Philips and GE dataset (leave-one-patient-out evaluation), respectively, and 0.96 and 0.89 when training on the GE dataset and testing on the Philips dataset, and vice versa, respectively. Spearman correlation coefficients between ROI-specific Gleason scores and the ADC features were between -0.27 and -0.34. This previous work (32) demonstrates that a pilot DSS tool developed based on data from Philips scanners can be effective with data from other scanners, and supports the feasibility of the proposed Risk Map DSS tool.

B. PURPOSE

The purpose of the proposed research is to test and validate **an artificial intelligence-based Risk Map decision-support system (DSS) for PCa MRI interpretation and identification of clinically significant tumor site based on MRI acquisition of a protocol covering the entire prostate which will include the kT-T2 and the hybrid multi-dimensional MRI (HM-MRI) sequences.**

We will test an artificial intelligence-based Risk Map DSS tool we have developed, which is based on and expanded from previously identified key MR image features that are effective for identifying PCa from normal prostate tissue, and which also correlates moderately with Gleason scores (ADC, T2, and tissue composition maps). The DSS tool will assist radiologists interrogate suspicious areas in the prostate that are potentially clinically significant PCa foci, and will identify up to two potential clinically significant tumor sites. In addition to systematic biopsies and the targets identified by the radiologist, up to two targets determined by the DSS tool will be biopsied. Biopsy histology results of all cores will be used as the reference standard to evaluate the performance of the Risk Map DSS tool.

C. METHODOLOGY

C.1. Study Design:

This is a prospective, single-arm, unblinded study of patients with known or suspected prostate cancer. A total of 125 patients will be enrolled.

Recruitment: We will recruit patients with known or suspected prostate cancer who have been referred to the Department of Radiology at the University of Chicago Medical Center for a diagnostic MRI exam of the prostate, to be followed by an MRI-guided fusion biopsy of the prostate, per standard clinical protocol.

All patients will be scanned using a standard clinical prostate MRI protocol. Research sequences will be added to the routine clinical exam. The research sequences will not exceed 15 minutes. The patients will not receive intravenous contrast agent as part of the research protocol.

All patients will then undergo a 12-core TRUS-guided or transperineal US-guided sextant random biopsy by their urologist at the Urology Clinic as their standard of care treatment. Additional biopsy targets may be selected based on an expert radiologist's interpretation of the patient's clinical MRI, as part of the clinical, standard of care MR targeted biopsy procedure. Up to two additional biopsy targets per patient will be selected by the Risk

Map DSS tool, if different from the already selected targets by the radiologist per standard of care. Ultimately, the clinical radiologist will make the final decision on the targets to be biopsied. MR-targeted biopsies will be done by using a Uronav MR-US fusion device. The following results will be recorded for each core: (1) the reason of biopsy (random biopsy; DSS tool alone; radiologist alone) (2) location (sextant and zone), and (2) histology result. Research cores will be evaluated by expert genitourinary pathologist, [name], and results will be communicated to the urologist.

Studies will be carried out using FDA approved 3 Tesla Philips, GE and Siemens MRI units at the University of Chicago Medical Center. All of the research MR sequences will be in compliance with FDA safety requirements and MR contrast agents will not be injected for research purposes.

C.2. MRI Data acquisition methods:

The data acquisition will consist of obtaining the standard clinical protocol and research sequences, in compliance with FDA safety requirements. Research sequences may include, but will not be limited to (1) KT-T2 sequence (high spatial resolution axial ME-TSE for T₂ measurements and anatomy visualization), and (2) axial HM-MRI with 4 b-values and 4 TEs for diffusion and T2 measurements. MR images will be acquired using Philips, GE or Siemens 3T clinical MR systems with a phased array surface receiver coil.

C.3. Study Endpoints and Statistical Analysis

The major goal of this study is to compare the accuracy of the Risk Map DSS tool against the clinical accuracy of experienced radiologists in the context of the reference standard of biopsy histology. The primary endpoints will be ROC curve, AUC value, the secondary endpoint will be sensitivity, specificity, PPV, and NPV, and the tertiary endpoint will be correlation strength between the DSS tool output and tumor-specific Gleason scores. Both per-patient and per-tumor analyses will be conducted. For the per-patient analysis, patients who are diagnosed with PCa from the biopsy procedure will be considered as positive for PCa, and patients who are not diagnosed with PCa from the biopsy procedure will be considered as negative for PCa. For the per-tumor analysis, each individual PCa tumor diagnosed from the biopsy procedure will be analyzed separately, and biopsy sites that do not yield PCa diagnosis will be considered as negative for PCa. To ascertain a true positive biopsy, the finding and the biopsy must match in sextant and zone. If ambiguity in biopsy site arises with regard to indications from the DSS tool, or the radiologist's opinion, and the biopsy, expert radiologist ([name]) and pathologist ([name]) will review each case to make the determination. This will allow us to calculate the performance of: (1) the Risk Map DSS tool, (2) the radiologist, and (2) the standard sextant biopsy. We will evaluate these performance endpoints on clinically significant PCa (but we will have data for all tumors). Spearman correlation coefficient will be estimated in the usual manner.

C.4. Statistical power consideration

We expect the following level of performance: AUC 0.90±0.03, sensitivity 90±5%, specificity 90±4%, and statistically significant (Spearman's) correlation strength of 0.8 with tumor-specific Gleason scores. Variances are estimated based on the expectation of PCa diagnosis in 35% of 125 patients, and based on an empirical rule-of-thumb formula

for AUC and binomial probability for sensitivity and specificity. The estimated 95% confidence intervals (CIs) are: for AUC [0.87, 0.93], for sensitivity [0.85, 0.95], and for specificity [0.86, 0.94]. These uncertainty estimates do not include analysis of biopsy by sextant and zone of the 12-20 cores per patient; estimates of 12 by-location-analyses per patient reduce all uncertainties to about 1%. These estimates suggest that this protocol will produce meaningful performance estimates.

D. DURATION OF THE PROTOCOL

The probable duration of the study will be 3 years with review, at least annually, to recruit the target number of patients and complete all data analysis.

E. LOCATION WHERE RESEARCH WILL BE CONDUCTED

The study will be conducted on the FDA approved 3 Tesla Philips, GE or Siemens MRI scanners at the University of Chicago Medical Center, [name].

F. SAFETY MONITORING

We do not anticipate any adverse events. However, adverse events related directly to the study will be reported to the Cancer Center Clinical trials office following standard operating procedures outlined in the Cancer Center data safety and monitoring plan.

G. DESCRIPTION OF EXPERIMENTAL CONTROLS AND USE OF PLACEBOS

N.A.

H. TYPE AND NUMBER OF EXPERIMENTAL SUBJECTS

We will recruit 125 patients who will receive a diagnostic MRI exam of the prostate, to be followed by an MRI-guided fusion biopsy of the prostate.

Inclusion Criteria

We will recruit patients with known or suspected prostate cancer who have been referred to the Department of Radiology at the University of Chicago Medical Center for a diagnostic MRI exam of the prostate, to be followed by an MRI-guided fusion biopsy of the prostate. Written informed consent will be signed by the patients before the MRI examination.

Exclusion Criteria

Subjects will be screened and excluded per standard clinical protocol.

Also excluded are:

- Subjects incapable of giving informed written consent;

- Subjects who cannot adhere to the experimental protocols for any reason, or have an inability to communicate with the researcher;
- Subjects with psychiatric disorders that affect their ability to consent for themselves will be excluded and not the entire population of patients with psychiatric disorders.
- Prisoners;
- Minor children (under the age of 18 years old).
- Previous treatments (surgery, radiation, focal ablation, hormone or other chemotherapy) for prostate cancer.

Data to be collected

Demographic information will be collected from each recruited subject. The research team will also collect clinic visit, laboratory, imaging and pathology results relevant to the clinical question for each subject.

J. SHARING RESEARCH RESULTS:

At times, the advancement of research or the development of healthcare devices is aided by the sharing of de-identified image data, pathology data, genetic data and clinical information with other organizations. De-identified copies of image data, pathology data, genetic data and clinical information may be sent outside of The University of Chicago for such purposes, including as part of an image library. If this occurs, scientists outside of The University of Chicago will be unable to identify the subject from medical images, pathology data, genetic data or from clinical information, because all identifying information will have been removed from the images and records. Insurance agencies will not have access to this information.

K. POTENTIAL RISKS AND BENEFITS TO SUBJECTS

Risks Associated with Magnetic Resonance Imaging

The risks below are the risks of standard MR imaging which the patients will undergo for clinical indications. The research component will not cause any additional risk to the existing minimal risks of clinical MR imaging. The research sequences will be designed in compliance with FDA requirements, and intravenous contrast material will not be administered for research purposes.

The presence of devices, implants, or other objects containing metal: Metal objects pose a serious risk to all patients undergoing MRI exams. This includes internally implanted objects such as surgical clips, biosupport devices (e.g., pacemakers), and artificial joints which contain metal.

Claustrophobia: Some individuals may experience claustrophobia during the MRI exam due to the limited space available inside the bore of the magnet.

Breach of confidentiality: There is a minimal risk that patient confidentiality may be breached.

Protection against risks associated with MRI

Protection against risks related to presence of metals, devices and other metal containing material: Participants are questioned carefully before MRI imaging to insure that they do not have metal implants. Prospective study participants who have such implants will be excluded from the study. Patients who have worked in or near machine shops and electronics shops and may have had metal slivers become trapped in their eyes, posing a potential hazard if exposed to a strong magnetic field, will also be excluded from the study. In addition, metal objects such as heavy key chains that are carried into the scan room can cause serious accidents. Participants will be cautioned to remove all metal objects before entering the scan room. Access to the scan room is carefully controlled to insure that no ferrous metal is inadvertently brought in.

Protection against claustrophobia: Prospective participants will be counseled about this possibility before the exam. The magnet is equipped with an intercom system enabling study subjects to communicate with the operators at any time during the exam. If they report any discomfort during the MRI examination they will be removed from the magnet immediately.

Protection against the breach of confidentiality: Patient identifiers will be kept and used only for the purpose of correlating patient data between radiology, urology and pathology. Patient identifiers will be removed from data analysis unless it becomes necessary to correlate results of the analysis to other clinical data, which we do not expect. Patient identifiers will be removed from all presentations and publications; only data from a group of patients will be reported so that data from any individual patient cannot be identified.

Risks associated with Transrectal and Transperineal Ultrasound-Guided Prostate Biopsy:

The risks will be those associated with standard MRI-guided fusion biopsy of the prostate, which the patients will undergo for clinical indications. The research component (upto two additional biopsy targets) will cause a minimal increase in the risk of bleeding and infection.

Benefits

There may or may not be any direct medical benefit to patients who are enrolled in the study.

There will be a long-term benefit to society in general if this research leads to the development of a new technology that improves clinical practice.

Alternatives

If patients decide not to participate in this study, they will undergo routine clinical examination ordered by their referring physician.

L. PAYMENT TO SUBJECTS

Patients will not be paid or compensated for their participation in this study.

M. OBTAINING WRITTEN CONSENT

The Principal Investigator or Co-Investigators or the Clinical Research Coordinator will be responsible for obtaining written informed consent signatures from the patients based on the research plan and consent form approved by University of Chicago Institutional Review Board.

Confidentiality will be insured by use of an encrypted patient ID numbering system for all research data to maintain confidentiality and anonymity.

N. CONFIDENTIALITY OF RECORDS

In accordance with the regulations promulgated by the Federal Food and Drug Administration, all records will be treated with strict adherence to professional standards of confidentiality. Care will be taken during the review of medical records to maintain as much privacy as possible. Only the treating physician or study staff will review the medical records. Records will be kept locked, and the database will have restricted access (password protected).

Security and Privacy:

This protocol is designed to respect proper attention to patient privacy and prevention of breach of confidentiality. For each patient, the study protocol number and the patient's medical record number will be entered into a restricted database by selected research personnel. Additional relevant general clinical information will be included. Access to the database will be password protected. All personnel are trained to maintain confidentiality of patient information according to HIPAA regulations. All of the images will be maintained in the password protected University of Chicago PACS.

Research charts, including signed consent forms, will be stored in a locked file cabinet in the clinical research coordinator's office at University of Chicago Medical Center, Room Q200. Although each chart, radiographic study, and MRI examination will contain the patient's name, and as such will not be anonymous, no individual identities will be used in any publications resulting from this study. Officials from examining bodies such as the U.S. Food and Drug Administration or NIH may inspect records pertaining to this study.

O. PATIENT RECRUITMENT:

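### C.3 does not define a DSS-positive site; if the nominated marks are scored, site-level DSS sensitivity and specificity depend on the two-mark limit and on the radiologist's target list

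*Combined protocol and SAP*

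**What the plan says.** Section B (Purpose) says the tool "will identify up to two potential clinically significant tumor sites". It describes the biopsied DSS targets, again at most two, as coming on top of the systematic cores and the radiologist's targets.

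C.1 (Study Design) words the rule differently. The radiologist's targets come first, with no number given: "Additional biopsy targets may be selected based on an expert radiologist's interpretation of the patient's clinical MRI". The next sentence begins "Up to two additional biopsy targets per patient will be selected by the Risk" and continues "Map DSS tool, if different from the already selected targets by the radiologist per standard of care". C.1 then adds: "Ultimately, the clinical radiologist will make the final decision on the targets to be biopsied".

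For each core, C.1 records "1) the reason of biopsy (random biopsy; DSS tool alone; radiologist alone". No category covers a site chosen by both.

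C.3 makes the comparison of DSS with radiologist the major goal. ROC curve and AUC are primary; sensitivity, specificity, PPV and NPV are secondary. Analyses are per patient and per tumor, and the matching rule is "To ascertain a true positive biopsy, the finding and the biopsy must match in sextant and zone". C.3 does not say what a DSS finding is: a nominated mark, a nominated mark plus sites shared with the radiologist, or a location above a threshold on the map.

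C.4 expects 90% sensitivity and 90% specificity, with variances based on cancer in 35% of 125 patients. It then adds that "estimates of 12 by-location-analyses per patient reduce all uncertainties to about 1" percent.

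**The concern.** Two readers are compared, but their marks follow different rules. The DSS may mark two sites; the radiologist has no stated limit. The DSS targets are also filtered through the radiologist's list, so the output of the tool under test may depend on the comparator. A site that both would choose stays on the radiologist's list, and the core record cannot show that the DSS chose it too.

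If nominated marks are what C.3 scores, part of any difference in site-level sensitivity or specificity comes from these rules and not from the image analysis. A third positive site counts as a DSS miss however high its map value, and the number of DSS false positives is limited by construction. The stake is how the secondary endpoints of the main comparison can be interpreted.

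**Working it through.** **1. The plan's own figures (C.4).** Positive patients: 0.35 × 125 = 43.75. The standard error of a 90% sensitivity is √(0.90 × 0.10 / 43.75) = 0.045, which is C.4's ±5% after rounding. The 90% is therefore set up as a per-patient figure. (C.4 presents this roughly one-standard-error range as a 95% interval; that is a separate matter.) At location level, 12 × 125 = 1500, of which 35% is 525 positive and 975 negative. The standard errors are √(0.09/525) = 0.013 and √(0.09/975) = 0.010, matching the stated figure of about 1%. This implies 525/43.75 = 12 positive locations in every positive man. I take that as a shortcut for the variance, not a forecast, and do not use it as a site count below.

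**2. Per patient.** One correct mark makes a positive man a true positive, so two marks impose no ceiling (100%).

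**3. Per tumor or location, scoring nominated marks.** Let K be the number of positive sites in a positive man. With at most two marks, each assumed to cover one site, the highest possible sensitivity is

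ceiling = E[min(K,2)] / E[K] = (2 − P(K=1)) / E[K].

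The nearest tumor count in the documents is 28 cancer regions in 21 patients (A.3.1), or 1.33 each. The distribution of K is not given, so two forms are assumed: geometric and zero-truncated Poisson. Worked case, geometric at a mean of 1.33: P(K=1) = 1/1.333 = 0.75, so the ceiling is (2 − 0.75)/1.333 = 0.9375.

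| Unit | K per positive man | Ceiling, geometric | Ceiling, truncated Poisson |
|---|---|---|---|
| Tumor | mean 1.33 | 93.8% | 95.4% |
| Tumor | mean 1.5 | 88.9% | 91.6% |
| Tumor | mean 2.0 | 75.0% | 79.7% |

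The ceiling passes below 90% at a mean of 1.46 (geometric) to 1.57 (truncated Poisson). If no man has more than two tumors it is 100%. For a constant number of positive locations it is 2/3 = 67% at three and 2/4 = 50% at four.

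At a mean of 1.33, a tumor-level sensitivity of 90% is possible, but the DSS would have to hit 0.90/0.954 = 94% to 0.90/0.9375 = 96% of the tumors it is allowed to mark.

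**4. Specificity.** In a cancer-free man, two wrong marks leave 1 − 2/12 = 83% with 12 sampled sites and 1 − 2/20 = 90% with 20 (C.4 gives 12–20 cores). This floor holds however poor the tool is. The radiologist has no such floor.

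**5. Shared sites.** Suppose a share s of the positive sites is already on the radiologist's list and those cores carry only the radiologist label. The sensitivity credited to the DSS from the core record is then at most 1 − s: 75% at s = 0.25, 50% at s = 0.50, 25% at s = 0.75. The documents give no value for s; these are illustrations. This loss arises even when every man has one tumor.

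**The case against.** The strongest reply is that the plan may never intend to score the nominations. The preliminary risk map in A.3.2 was thresholded over all sectors: it detected 105 sectors in 17 patients, 6.2 each, which two marks per man could not produce. Section B makes all cores the reference standard, and a primary ROC analysis needs a graded score. Scored in that way, the two-site limit only guides biopsy and nothing is capped. This is a fair inference about intent, but C.3 does not state it, and its matching rule is written in terms of findings. C.3 also sends ambiguous sites to expert review. That helps only if the DSS's own sites were stored.

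The if-different clause can also be read as plain de-duplication: no second core where the radiologist already has a target. A reader might instead infer that the DSS replaces shared sites with its third and fourth choices. No passage says so. Both readings are open, and under the replacement reading with shared sites credited, a limit of two would not apply.

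A reader might further infer that C.4's 90% sensitivity is unreachable, for example by setting two marks against the 140 positive sectors in 17 pilot patients. The documents do not support that. The 90% rests on patient counts, C.3's unit is the tumor, and one tumor can span several sectors. The sector count also comes from a preoperative cohort.

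Nor does the imbalance justify cutting the radiologist to two targets. C.3 aims to measure the radiologists' clinical accuracy, and a truncated list would not do so.

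**Conclusion.** The point holds, conditionally. The limit on DSS sites, the filter through an unlimited radiologist list, the missing category for shared sites and the undefined DSS-positive call are all in the text. If nominated marks are scored, secondary per-tumor or per-location DSS sensitivity and specificity depend partly on those rules.

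The size depends on the unit. Per patient, two marks impose no ceiling. Per tumor, the ceiling is about 94–95% at the pilot's 1.33 and falls below 90% from a mean of about 1.5. Per location, it is 67% at three positive sites and 50% at four. The tumor-level figures rest on assumed distributions and on preoperative patients; biopsy patients, assessed for clinically significant cancer, may have fewer positive sites. The primary AUC is unaffected if it uses the map value at every site. The plan should be clarified, but C.4's 90% is not shown to be out of reach.

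**What to change.** In C.1:
- Generate and store the DSS sites before the radiologist's targets are known to the tool, and without reference to them, with one rule for their number.
- Reconcile Section B's limit on sites with C.1's limit on additional targets.
- Let overlap decide only whether a separate core is needed, not which sites the DSS is credited with.
- Add a category to the core record for sites chosen by both.

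In C.3:
- Score the DSS at every sampled sextant-zone location from its Risk Map value there.
- Fix in advance the threshold that turns this value into a positive call for sensitivity, specificity, PPV and NPV.
- State that the two nominations serve only to guide biopsy.
- Keep the radiologist's full target list in the comparison.

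The cost is protocol wording, one more code in the core record, and storage of map values the tool already produces. No extra patients or cores are needed. The change should be made prospectively: an independent DSS list that was never stored cannot be reliably reconstructed later.
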